All data will be managed using REDCap⁶⁵, MS 365 Excel 16.54 (Microsoft, USA), and MATLAB R2020a (Mathworks Inc, USA) and will be analyzed using SPSS[®] Statistics 26 (64-bit edition, IBM, USA). Descriptive statistics, including means, standard deviations and 95% confidence intervals of the within-participant pre-post change for each intervention will be calculated for all measures. The baseline characteristics of the participants will be compared using parametric and non-parametric inferencing.

Hypothesis testing: To evaluate our main hypothesis that caffeine prior to AIH enhances walking recovery, we will perform a linear mixed model with fixed effects at a significance at the p=0.05 level.⁶⁶ Intervention (caffeine+dAIH, caffeine+SHAM, placebo+dAIH) and time (day) will be the fixed main effects, with subject as random effect and walking speed (10MWT) as repeat measures. Differences from BL will be compared between and within interventions at D₅, F₁, and F₂. Bonferroni corrections will be made for multiple comparisons. If distributions are not normal, we will perform comparable nonparametric tests. If baseline measures are significantly different between sessions (interventions), an analysis of co-variance (ANCOVA) will be used to analyze the data. We predict walking speed (10MWT) will be greater after daily caffeine+AIH as compared to after daily placebo+AIH and daily caffeine+SHAM.

Blinding integrity analysis: we plan to rigorously quantify blinding integrity here. We will ask participants and raters to guess the intervention received at the end of each intervention and indicate guess confidence using a Likert scale.^{67,68} We will use a contingency table and Fischer's

DETAILED STUDY PROTOCOL

Exact Test to determine if the probability of correct guessing is different from chance. Using multivariate logistic regressions, we also will assess factors that may influence guessing (i.e., adverse events, perceived effects, and sensorimotor changes). In the event of a medical emergency, we will unblind the PI, study participants, and care provider. We also will notify IRB of treatment allocation during adverse event reporting as necessary.

V. Monitoring

21. Data monitoring

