- Concealment mechanism – We will conceal the intervention allocation from the evaluators performing the assessments, treatment administrators, and the study participant.
- Implementation – The PI and biostatistician will generate the allocation sequences for the cross-over study. The trial coordinator will enroll participants and study staff who are not training or assessing the participants will assign the block randomized interventions.

11. Sample size

Twenty individuals with chronic (> 6 months post injury), motor-incomplete SCI (i.e., American Spinal Injury Association Impairment Scale (AIS) C or D) will be recruited for the study. Prior to the start of this clinical trial, we estimated the number of participants needed to achieve study objectives. In particular, our sample size computation focused on treatments: caffeine+dAIH versus placebo+dAIH alone. Our preliminary study on the effects of caffeine prior to single AIH sequence (vs placebo+SHAM) on 10MWT showed a decrease of 2.4s±1.2s. Under the hypothesis of an additive effect of caffeine+dAIH (vs. placebo+dAIH), we anticipate the difference in walking speed (10MWT time) change between treatments would be approximately 0.06m/s. With N=20 cross-over participants (includes 17% attrition rate), a repeated measures ANOVA comparing 4 treatments across 4 time points, using pooled SD of 1.3s across days, will be sensitive to detect a difference at power of $1 - \beta = 0.80$ ($f=0.7$, $F_{3,12}=3.5$; $p=0.4$, $\alpha=.05$).

12. Framework

This placebo-controlled study will examine the combined effects of caffeine and AIH results in greater walking performance than either intervention alone. However, this trial will not evaluate the potential superiority or equivalence of caffeine+AIH to standard of care treatments for persons with chronic iSCI.

13. Statistical interim analyses and stopping guidance

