We do not plan to conduct an interim analysis. However, we will impose criteria for discontinuing or modifying allocated interventions. The interventions will be stopped, and immediate care provided if any significant adverse effects, such as rapid heart rate, dizziness, nausea, or a significant change in blood pressure, are detected or self-reported by the study participant. Participants with diabetes, cirrhosis, a history of autonomic dysreflexia, caffeine allergies or sensitivities, or females who are pregnant will be excluded from this portion of the study. Due to the diuretic effects of caffeine, subjects will be asked to empty their bladders prior to consumption. During and between interventions, blood pressure and heart rate will be monitored. Any adverse effects will be reported and assessed. Our study team will be prepared to discontinue treatment and offer immediate care if any significant adverse effects, such as rapid heart rate, systemic hypertensive event, dizziness, or nausea are detected or self-reported by the subject. We will define a systemic hypertensive event as a systolic pressure exceeding 140 mmHg and/or diastolic pressure exceeding 90 mmHg.^{24, 25} We will stop this trial if serious adverse events are directly attributed to the interventions under study.

14. Timing of analysis

All outcomes will be analyzed collectively. We will maintain concealment of the intervention allocation until the completion of data collection.

15. Timing of outcome assessments

Timing of outcome assessments will occur during specified visits. The timepoints of these assessments along with the timepoints for enrollment and interventions are detailed in the timing schedule (Table 1).

Table 1. Timing Schedule for enrollment, interventions, and assessments

Timepoints (days)	Enrollment		Baseline		Intervention			Follow-ups/Washout	
	-5	0	1	2	3	4	5	8	14
Screening and Allocation Timing									
Eligibility screen	x								
Informed consent	x								
Medical clearance	x								
Allocation		x							
Drug script		x							
Intervention Timing									
Placebo+AIH			x	x	x	x	x		
Caffeine+AIH			x	x	x	x	x		
Caffeine+SHAM			x	x	x	x	x		
Assessment Timing									
Primary outcome									
• Walking speed (10MWT, s)		x				x	x	x	
Other outcomes									
• Voluntary leg strength	x				x	x	x	x	
• Spasticity	x				x	x	x	x	
• Spasm frequency	x				x	x	x	x	
• Walking function	x				x	x	x	x	
• Walking distance (6MWT, m)	x				x	x	x	x	
• Walking Balance (TUG, s)	x				x	x	x	x	

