• Blinding Questionnaire		x	x	x	x	x			
• Weight (kg)	x						x	x	
Safety Outcomes									
• Pain (0-10)	x	x	x	x	x	x	x	x	
• Blood pressure (mmHg)	x	x	x	x	x	x	x	x	
• Heart rate (BPM)	x	x	x	x	x	x	x	x	
• Oxygen saturation (%)	x	x	x	x	x	x	x	x	
• Memory (0-30)	x	x	x	x	x	x	x	x	
Biomarkers									
• CYP1A2 Polymorphism	x								
• Caffeine serum level (mg/L)		x				x			
• Inflammation (CRP)		x			x		x		

IV. Statistical Principles

We plan to use a parametric linear mixed model since this method is sensitive to within subject changes and robust against variability, small sample sizes, and missing/unbalanced data sets as compared to other statistical models.²⁶ If the results do not meet these model assumptions, we will apply alternative non-parametric tests.

16. Level of significance

All applicable statistical tests will be 2-sided and will be performed using a 5% significance level.

17. Adjustment for multiplicity

we do not plan to adjust for multiplicity.

18. Confidence intervals

Statistical comparisons will include 95% (2-sided) confidence intervals (CIs).

19. Adherence and protocol deviations

We will record a deviation (if the even does not significantly affect a participant's rights, safety, or well-being, or trial outcomes), or a violation (if the deviation may potentially significantly impact the completeness, accuracy, and/or reliability of the trial data or that may significantly affect a patient's rights, safety, or well-being). All protocol deviations/violations will be logged, but no formal statistical testing will be performed.

Adverse events will be reported on an IRB-approved electronic Case Report Form (eCRF). Details will include the type of event, date of onset, duration, intensity, causality relationship to the study drug(s), and outcome. If an adverse event should occur, every attempt will be made to obtain as much information as possible about event evaluation and outcome. If a serious adverse event occurs, the treatment will be interrupted or discontinued at the physician investigator's discretion. All protocol deviations will be reported to the PI ([name]) and the IRB.

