We will quantify secondary measures of walking function using the timed up-and-go test (TUG, walking initiation and balance), six-minute walk test (6MWT, walking endurance). These tests capture functional ambulation as well as the ability to initiate walking, exhibit high reliability and construct validity.³⁵ Participants will perform 2 trials each of the TUG at their fastest but comfortable and safe speed with a minimum of 1-minute rest between trials. Average speed across the 2 TUG trials will be used for analyses. Subjects will perform the 6MWT once at their fastest, comfortable walking speed sustainable for 6 minutes. Distances will be recorded at 2 and 6 minutes. Participants will use their least restrictive assistive device during these walking assessments.

27. Analysis methods

We plan to analyze within-participant pre-post changes in walking speed (10MWT) for each intervention. We plan to use a parametric linear mixed model for comparing our outcome measure since this method is sensitive to within subject changes and robust against variability, small sample sizes, and missing/unbalanced data sets as compared to other statistical models.²⁶ If the results do not meet these model assumptions, we will apply alternative non-parametric tests.

All data will be managed using REDCap³⁶, MS 365 Excel 16.54 (Microsoft, USA), and MATLAB R2020a (Mathworks Inc, USA) and will be analyzed using SPSS[®] Statistics 26 (64-bit edition, IBM, USA). Descriptive statistics, including means, standard deviations and 95% confidence intervals of the within-participant pre-post change for each intervention will be calculated for all measures. The baseline characteristics of the participants will be compared using parametric and non-parametric inferencing.

Hypothesis testing: To evaluate our main hypothesis that caffeine prior to AIH enhances walking recovery, we will perform a linear mixed model with fixed effects at a significance at the p=0.05 level.³⁷ Intervention (caffeine+dAIH, caffeine+SHAM, placebo+dAIH) and time (day) will be the fixed main effects, with subject as random effect and walking speed (10MWT) as repeat measures. Differences from BL will be compared between and within interventions at D₅, F₁, and F₂.

Bonferroni corrections will be made for multiple comparisons.

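### The SAP both rules out and requires multiplicity adjustment for the primary 10MWT comparisons, and no primary visit or family size is stated, so a comparison with p = 0.03 can be called positive or negative

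*Combined protocol and SAP*

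**What the plan says.** SAP 16 sets the level: "All applicable statistical tests will be 2-sided and will be performed using a 5% significance level". SAP 17, the section that governs multiplicity, then says "we do not plan to adjust for multiplicity". It is not limited to any outcome or comparison.

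SAP 27 and protocol 20 describe the 10MWT mixed model and continue: "Differences from BL will be compared between and within interventions at D₅, F₁, and F₂". The next sentence in both is "Bonferroni corrections will be made for multiple comparisons".

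SAP 26 defines the primary outcome as change in 10MWT from baseline, using BL, D5, F1 and F2, and names no primary visit.

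On what counts as success, the text points in two directions:

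- SAP 11 and protocol 14 size the trial on one pair: "our sample size computation focused on treatments: caffeine+dAIH versus placebo+dAIH alone".
- SAP 12 speaks of "greater walking performance than either intervention alone", and protocol 20 adds "We predict walking speed (10MWT) will be greater after daily caffeine+AIH as compared to after daily placebo+AIH and daily caffeine+SHAM". Both point towards beating two comparators.

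None of these is written as a rule for declaring success.

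**The concern.** The Bonferroni sentence directly follows the 10MWT comparisons, so it applies to the primary analysis. SAP 17 does not exempt the primary analysis from its statement. The SAP therefore contradicts itself and the protocol on the same tests, and either sentence could be cited once the p-values are known.

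Choosing Bonferroni would not by itself settle the matter, because the divisor is not given and plausible families run from 2 to 18 tests. Choosing no adjustment would not settle it either. The sized contrast is tested at three visits, and the text does not say which one decides. The sample size statement uses an undivided alpha of .05, so it makes no allowance for Bonferroni.

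**Working it through.** **The plan's own figure.** SAP 11 states power 0.80 with f = 0.7, F(3,12) = 3.5 and alpha .05. The critical value of F(3,12) at 0.05 is 3.490, so the 3.5 is an undivided 5% threshold. Power of 0.80 was not reproduced. If the printed p = 0.4 is read as a correlation of 0.4 (an assumption), the nearest variants give 0.773 (between-factor, N = 16) and 0.831 (within-factor, n = 5). That is a separate matter, and nothing below depends on it. The N is consistent: 16/(1 − 0.17) = 19.3, rounded up to 20. Conversely, 20 × 0.83 = 16.6, taken as 17 completers.

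**Number of comparisons.** Between interventions: 3 pairs × 3 visits = 9. Within interventions: 3 × 3 = 9 changes from baseline. Total: 18.

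**What each rule does with p = 0.03.** The Bonferroni threshold is 0.05/k and the adjusted p is 0.03 × k.

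| Family | k | Threshold | Adjusted p | Bonferroni | No adjustment |
|---|---|---|---|---|---|
| Two contrasts, one visit | 2 | 0.025 | 0.06 | negative | positive |
| One contrast, three visits | 3 | 0.0167 | 0.09 | negative | positive |
| Two contrasts, three visits | 6 | 0.0083 | 0.18 | negative | positive |
| All between-intervention | 9 | 0.0056 | 0.27 | negative | positive |
| All between and within | 18 | 0.0028 | 0.54 | negative | positive |

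This step needs no assumption about the data.

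**Effect of the open visit (illustrative).** 40,000 simulated crossovers per setting; 17 completers; 3 interventions × 4 visits; unit visit errors; post-treatment errors correlated 0 / 0.5 / 0.8 within an intervention (assumed). Each contrast is the difference between interventions in change from baseline, tested two-sided at 0.05 and counted when it favours caffeine+dAIH. The mixed model has a random subject intercept and intervention-by-visit means. The interaction is assumed, because the plan compares interventions at each visit.

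| Favourable false-positive rate for caffeine+dAIH over placebo+dAIH, no adjustment | Mixed model | Paired t |
|---|---|---|
| Sized contrast, one fixed visit | 2.4 / 2.9 / 3.2% | 2.4 / 2.4 / 2.4% |
| Sized contrast, any of three visits | 6.2 / 6.0 / 5.5% | 6.4 / 5.3 / 4.3% |
| Both contrasts, same free visit, nothing works | 1.4 / 1.3 / 1.4% | 1.3 / 1.0 / 0.8% |
| Both contrasts, same free visit, caffeine+SHAM truly beaten | 6.1 / 6.0 / 5.3% | 6.3 / 5.2 / 4.2% |
| Both contrasts, one named visit, caffeine+SHAM truly beaten | 2.5 / 2.9 / 3.3% | 2.5 / 2.4 / 2.4% |

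Caffeine+SHAM truly beaten means by 4 error SD (assumed). For the sized contrast at any of three visits under the mixed model, p falls between 0.0167 and 0.05 in 4.1 / 3.7 / 3.4% of trials. That is 4.1/6.2 = 66%, 3.7/6.0 = 62% and 3.4/5.5 = 62% of the false positives. In that range the two rules disagree for k = 3.

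**Power cost of Bonferroni.** Paired contrast, n = 17, effect d in SDs of the within-person difference (assumed). Power is from the non-central t, equivalently F(1,16) with non-centrality 17d².

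| d | k = 1 | k = 3 | k = 9 | k = 18 |
|---|---|---|---|---|
| 0.6 | 64% | 44% | 28% | 20% |
| 0.724 | 80% | 63% | 44% | 34% |
| 1.0 | 97% | 91% | 80% | 71% |
| 1.2 | 100% | 98% | 94% | 89% |

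**The case against.** - **The sentences can be reconciled.** SAP 17 is a general statement of principle, while the Bonferroni sentence is specific and appears in both documents. Bonferroni could govern the 10MWT comparisons and SAP 17 the other outcomes. This is a sensible reading, but the documents do not state it, and it still leaves the family size and the visit open.
- **The deciding test could be the overall intervention effect.** In that case p = 0.03 would be positive under both rules. This is correct, and the conflict concerns the comparisons at D5, F1 and F2. Those are the comparisons the plan lists and the ones that bear on its prediction about caffeine+dAIH.
- **The simulation goes beyond the text.** SAP 27 names main effects only, and nothing in it permits picking a visit. Part of the mixed-model excess (2.9% and 3.2% at one fixed visit) comes from visit correlation that a random intercept does not model. This stands. The paired t results isolate the effect of the visit choice: 2.4% rising to 4.3–6.4%.
- **The power loss depends on the effect.** If f = 0.7 is read as a two-level contrast (d = 1.4, an assumption), power is 100 / 99.8 / 98.8 / 97.4% for k = 1 / 3 / 9 / 18. With a large effect, Bonferroni would cost little. The units in SAP 11 (0.06 m/s with an SD in seconds) do not allow the effect to be pinned down.
- **The remedy is wider than the contradiction.** Reconciling one sentence and stating the family would remove the clash. It would not say which result decides the trial.

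**Conclusion.** The concern holds. The current text gives two incompatible rules for the primary 10MWT comparisons, and the visible text supplies neither a primary visit nor a family size. On any of those comparisons, a p-value between 0.05/k and 0.05 leads to opposite conclusions for every k of 2 or more. That conclusion rests on the wording and on division alone.

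The size of the inflation is illustrative. With 17 completers, assumed visit correlations of 0 to 0.8 and a free unadjusted choice of visit, the favourable false-positive rate on the sized contrast is 4.3–6.4% against a nominal 2.5%. Requiring both contrasts does not remove the need to name the visit: the rate is about 1% if nothing works, but 4.2–6.3% if caffeine+SHAM is truly beaten. The power cost of Bonferroni ranges from severe to negligible over the effects considered. This must be fixed, because the rule that decides the trial is undefined.

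**What to change.** Delete the SAP 17 sentence or limit it to named secondary analyses. Then state the following in the same words in SAP 17, SAP 27 and protocol 20, before unblinding:

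1. One primary visit, chosen by the sponsor.
2. The primary contrast or contrasts, saying whether caffeine+dAIH must beat placebo+dAIH only or both comparators, consistent with SAP 12.
3. The error control. If both contrasts must succeed at the named visit, each can be tested at two-sided 0.05 without division. If one is enough, use a fixed sequence starting with the sized contrast, or Bonferroni over a stated family.

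Other visits, the comparison between the two control interventions and the within-intervention changes become secondary.

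**Cost.** Wording only, if done in time. Secondary comparisons could then not support a claim by themselves. Requiring both contrasts lowers power from 80% to 69% at 0.724 SD and from 64% to 48% at 0.6 SD (equal effects and contrast correlation 0.5 assumed).

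**Timing.** SAP 14 says "We will maintain concealment of the intervention allocation until the completion of data collection". The documents do not say whether that point has passed, although the past tense used for recruitment in protocol 10 and SAP 22, and for blood sampling in protocol 33, suggests the trial was already under way. If allocation has been revealed, the new rule cannot be called prespecified, and results under both rules should be reported.

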26. Outcome definitions

The primary outcome measure is change in walking speed (10MWT time, s) relative to baseline (BL). For all analyses, we will use the average of two 10MWT times at BL, D₅, F₁, and F₂. Change

in walking speed will correspond to the difference between post-intervention 10MWT and BL times. Please review Table 1 for timing of outcome assessments.

All the summaries in this section will be equivalent to the main and the final results reports. There will be statistical testing completed for baseline testing of the primary outcome measure (10MWT). Since we plan to use a cross-over study design, we will compare the 10MWT baseline measurements between the interventions to evaluate the effects of the washout period.

Assessment and collection plans: Physical evaluations will be completed by the study's licensed physical therapists or occupational therapists and/or trained research study staff. Functional ability of subjects will be evaluated using standard clinical assessments with high inter-rater reliability: American Spinal Injury Association Impairment Scale (AIS) lower extremity motor scores (LEMS) to quantify strength,²⁸ and Spinal Cord Assessment Tool for Spastic Reflexes (SCATS), and the Penn Spasm Frequency Scale (PSFS) which is a self-report assessment of the frequency and severity of muscle spasms²⁹ and modified Ashworth Scale to quantify spasticity.³⁰ We also will record pain severity using the well-established Wong-Baker FACES scale, which shows high test-retest reliability and interpretability as well as good content and construct validity.^{31,32} Clinical ratings of walking ability, including Walking Index for Spinal Cord Injury (WISCI) II³³ and/or SCI Functional Ambulation Index (SCI-FAI),³⁴ will be assessed based on video recordings of the 10MWT.

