Alternative statistical methods: If distributions are not normal, we will perform comparable nonparametric tests. If baseline measures are significantly different between sessions (interventions), an analysis of co-variance (ANCOVA) will be used to analyze the data.

Blinding integrity analysis: we plan to rigorously quantify blinding integrity here. We will ask participants and raters to guess the intervention received at the end of each intervention and indicate guess confidence using a Likert scale.^{38,39} We will use a contingency table and Fischer's Exact Test to determine if the probability of correct guessing is different from chance. Using multivariate logistic regressions, we also will assess factors that may influence guessing (i.e., adverse events, perceived effects, and sensorimotor changes). In the event of a medical emergency, we will unblind the PI, study participants, and care provider. We also will notify IRB of treatment allocation during adverse event reporting as necessary.

CYP1A2 analysis: we will perform subgroup analysis on our study cohort to determine the extent to which differences in caffeine metabolism due to CYP1A2 polymorphisms may affect responsiveness to the combinatorial treatment of caffeine+AIH.

28. Missing data

Rigorous efforts will be made to ensure complete outcome data. However, we anticipate that participants in this study cohort may be unable to complete the study requirements. Missing data will be reported and documented as we did in our previous clinical trial.⁴⁰ We will document reasons for missing data and our approach to handle missing data during statistical analysis. We will account for potential outliers in our results using a conservative outlier labeling technique set forth by Hoaglin and Tukey.⁴¹

29. Additional analyses

We do not anticipate any additional statistical analyses methods.

30. Harms

Checklists and note pages are used to log any deviations or omissions from the protocols. Any clinical/health related issues would be immediately presented to the subject to determine appropriate notification (i.e., current physician or appropriate specialist). Based on the seriousness of the situation Drs. [name] or [name] may be contacted to provide clinical guidance on the appropriate course of action as per our Laboratory Medical Emergency Safety Plan.

31. Statistical software

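### The stated crossover model has no intervention-by-visit term, so it cannot give the promised differences at D5, F1 and F2, and baseline adjustment hangs on a significance test

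*Combined protocol and SAP*

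**What the plan says.** SAP section 27 (Hypothesis testing) and Protocol section 20 describe the same mixed model. Intervention has three levels, and "time (day) will be the fixed main effects, with subject as random effect and walking speed (10MWT) as repeat measures". The text then continues: "Differences from BL will be compared between and within interventions at" D5, F1 and F2, followed by "Bonferroni corrections will be made for multiple comparisons". SAP section 17, in contrast, says that no multiplicity adjustment is planned.

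The response variable has to be inferred. SAP section 26 defines the primary outcome as the change in 10MWT from baseline, and section 27 opens with "We plan to analyze within-participant pre-post changes in walking speed (10MWT) for each intervention". The sample-size text (SAP section 11, Protocol section 14) instead refers to "a repeated measures ANOVA comparing 4 treatments across 4 time points", which counts baseline as a level of time.

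Baseline is handled in two places. SAP section 26 says "we will compare the 10MWT baseline measurements between the interventions to evaluate the effects of the washout period". SAP section 27 (Alternative statistical methods) and Protocol section 20 say "If baseline measures are significantly different between sessions (interventions), an analysis of co-variance (ANCOVA) will be used to analyze the data". Neither document names an intervention-by-visit term, a period term or a within-period covariance.

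**The concern.** The model and the comparisons promised from it do not match. A model with only main effects for intervention and time assumes that the gap between interventions is the same at every visit. The trial treats for five days and then follows participants to day 14, so whether an effect fades is part of the question. An analyst who fits the model as written tests an average over visits. One who adds an interaction tests something else. The plan does not say which is primary.

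Two further choices are open. The three change scores of one period subtract the same baseline measurement, so they are correlated, and a random participant effect alone does not capture that. Also, the rule of using ANCOVA only when baselines differ significantly means the more precise analysis is almost never used, in a trial of about 17 to 20 participants.

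**Working it through.** **The plan's own figure.** With 16 completers in four groups, f = 0.7, four time points and the printed 0.4 read as a correlation (my assumption), the noncentrality is 0.49 x 16 x 4 / (1 + 3 x 0.4) = 14.25. The critical F(3,12) is 3.49, as printed (3.5), and 16/0.83 = 19.3 rounds up to 20. Power is 0.773 against the stated 0.80; f = 0.722 would give 0.80, so rounding may explain the gap. Nothing below depends on it.

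**1. What the additive model can return.** Write the mean as intercept + a(intervention) + b(time).
- *Change as response (visits D5, F1, F2).* The difference between two interventions is a1 - a2 at every visit, estimated by the average over the three. A D5-only effect gives (1 + 0 + 0)/3 = 0.33, a fading one (1 + 0.5 + 0)/3 = 0.50, a constant one 1.
- *Baseline as a fourth time level.* The difference in change at D5 is [(a1 + bD5) - (a1 + bBL)] - [(a2 + bD5) - (a2 + bBL)] = 0, whatever the data. The same holds at F1 and F2.

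**2. Error term.** Assumptions, because the SAP states no covariance: independent visit errors with variance s², residuals independent given participant, n = 17.
- Each change has variance 2s², and two changes in one period share covariance s², so their correlation is 0.5.
- The period-level mean square is 3 x (s²/3 + s²) = 4s² on 2 x 16 = 32 df. The within-period mean square is s² on 17 x 3 x 2 = 102 df, less 2 for visit and, if fitted, 4 for the interaction.
- *D5 contrast, interaction model.* Pooled residual (32 x 4 + 96)/128 = 1.75s². Claimed variance 2 x 1.75s²/17 = 3.5s²/17; true variance 2 x 2s²/17 = 4s²/17. Effective critical value 1.96 x √(3.5/4) = 1.83, so type I error is about 0.067.
- *Contrast averaged over visits, additive model.* Pooled residual (32 x 4 + 100)/132 = 1.727s². Claimed variance 2 x 1.727s²/(3 x 17) = 1.152s²/17; true variance 2 x (4/3)s²/17 = 2.667s²/17. Effective critical value 1.96 x √(1.152/2.667) = 1.29, so type I error is about 0.20.
- Simulation (40,000 runs per case) gives 0.067 and 0.195 to 0.197. Adding participant-by-period brings the D5 contrast to 0.049 to 0.053.

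**3. The baseline rule.** Without carryover, a 5% test triggers ANCOVA about 5% of the time, so about 95% of such trials keep the unadjusted change score. For within-person correlation r between baseline and outcome (assumed; the documents give none), the variance of ANCOVA relative to the change score is (1 - r²)/[2(1 - r)] = (1 + r)/2, that is 0.60, 0.75 and 0.85 at r = 0.2, 0.5 and 0.7. Simulation at D5 (40,000 runs per case; participant, intervention and period fixed) gave:

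| r | Type I error, plan's rule | Power, plan's rule | Power, always adjusted |
|---|---|---|---|
| 0.2 | 0.043 | 80% | 94% |
| 0.5 | 0.046 | 80% | 88% |
| 0.7 | 0.049 | 80% | 84% |

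**4. Which adjustment delivers that gain.** The always-adjusted column treats participant as fixed, so the baseline slope is purely within-person. With a random participant and only the period's baseline, the slope mixes within- and between-person relations and is pulled toward zero when people differ widely. At r = 0.2 and an assumed between-person SD of 5 visit SDs, power goes from 81% to only 83%. Adding the participant's mean baseline, or fixing participant, gives 95%.

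**The case against.** The strongest reply is that the sentence after the model names visit-specific contrasts, so an interaction, or separate comparisons of change scores at each visit, is probably what is meant. Nothing in the documents forbids it. That is fair, and the dilution figures apply only to an analyst who fits the model literally. What stands is that the written model does not contain the promised contrasts, and a SAP should not leave this to be guessed.

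A reader might infer that the primary test is badly anti-conservative. The documents do not support that. They state no covariance, and calling 10MWT a repeated measure hints at some structure without defining one. For the visit-specific contrasts the SAP names, the excess under the assumptions above is about 0.07 against 0.05; the 0.20 belongs to an averaged contrast. Familywise error rates cannot be quoted, because the SAP never counts its contrasts and sections 17 and 27 disagree on whether to adjust at all.

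A reader might also infer that the ANCOVA rule inflates type I error or leaves baseline out. It does neither: the simulated error stays below 0.05, and a change score already subtracts the period's baseline. Only covariate adjustment is lost.

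Nor does the text show harm from using the baseline comparison to judge washout. Carryover that is equal across interventions cancels from the contrasts under balanced orders, and sensitivity to unequal carryover depends on a set of sequences that SAP section 10 does not state.

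**Conclusion.** The point holds as a gap in specification that should be fixed, with moderate confidence. The mismatch between the additive model and the visit-specific contrasts is algebra and needs no assumed figure. Its consequence, if the model is fitted literally to change scores, is that 33% of a D5-only effect or 50% of a fading one is returned. The type I error figures (about 0.07 at D5, about 0.20 averaged) rest on independent visit errors and on residuals taken as independent given participant, neither of which the SAP states. The power given up by the baseline rule (about 14, 8 and 4 percentage points at correlations of 0.2, 0.5 and 0.7) rests on assumed correlations, and is recoverable in full only if the participant's mean baseline, or a fixed participant effect, is in the model.

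**What to change.** Pre-specify one model and use it whatever a baseline test shows:
- Response: change in 10MWT from that period's baseline, at D5, F1 and F2.
- Fixed effects: intervention, visit, intervention x visit, period, that period's baseline, and the participant's mean baseline across periods (or participant as a fixed effect in place of the mean).
- Random effects: participant and participant-by-period, or a stated within-period covariance, with Satterthwaite or Kenward-Roger degrees of freedom.
- Primary test: caffeine+AIH versus placebo+AIH at one named visit, taken from intervention x visit.
- Delete the rule that brings in ANCOVA only after a significant baseline difference.
- Reconcile SAP sections 17 and 27 on multiplicity, and list the contrasts that any Bonferroni correction covers.

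The cost is SAP and protocol wording and about eight fixed-effect degrees of freedom (4 for the interaction, 2 for period, 1 for each baseline term). All the variables are already collected and a mixed model is already planned. There is one real trade-off: if the effect is constant over visits, a single-visit contrast has less power than an averaged one (81% against 93% in the change-score simulation, with the correct error term). If the effect is D5-only or fading, the averaged contrast falls to 21% or 40%. The sponsor should choose the visit, or the average, on the expected time course and write it down.
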